## 4.11 Cumulative dosage

The cumulative dosage of the study drug is defined by the following formula.

Cumulative dosage of MT-6548 = 150 mg × Days of 150 mg administration + 300 mg × Days of 300 mg administration + 450 mg × Days of 450 mg administration + 600 mg × Days of 600 mg administration

Number of administration days of X mg\* = Day when dose was changed from X mg – First day of X mg administration (not excluding the number of days of no drug administration)

If there are multiple applicable periods, the sum of them should be used.

\*: X indicates each dose of MT-6548.

#### 4.12 Hb value increase rate

The Hb value increase rate (g/dL/week) is defined as the rate calculated using the following method.

- Hb value increase rate (g/dL/week):  
(Hb value at Week 4 of the treatment period – Hb value at the first day of the treatment period)/([Hb value measurement day at Week 4 of the treatment period – Hb value measurement day at the first day of the treatment period]/7)
- Hb value increase rate (regression) (g/dL/week):  
The slope of the regression line calculated based on the Hb values measured from the first day of the treatment period to Week 6 of the treatment period and the measurement day (number of weeks from the first day of the treatment period) is defined as the Hb value increase rate (regression). Subjects without data at the first day and Week 6 of the treatment period should be excluded from the tabulation. The number of weeks from the first day of the treatment period used to obtain the regression line is defined by the following formula.

First day of the treatment period: 0

Treatment period of Week 2: (Measurement day at Week 2 of the treatment period – First day of the treatment period)/7

Treatment period of Week 4: (Measurement day at Week 4 of the treatment period – First day of the treatment period)/7

Treatment period of Week 6: (Measurement day at Week 6 of the treatment period – First day of the treatment period)/7

Unscheduled study visit from the first day of the treatment period to Week 6 of the treatment period: (Day of unscheduled study visit – First day of the treatment period)/7

#### 4.13 Iron supplement dosage

The dose of iron supplements is defined by the following formula.

Mean monthly dose of iron supplements during the screening period\* and each scheduled study visit period\* (tabulation period of iron supplements) = (Daily dose based on the physician's prescription × Period of administration (days) of the corresponding dose\* during the tabulation period of iron supplements)/Tabulation period of iron supplements (days)\* × 30.4375\*

- \*: The number of days of the screening period is “First day of the treatment period – First day of the screening period”.
- \*2: For each period between the scheduled study visits, the actual study visit dates are not considered, and this tabulation is fixed as follows:
  - The first day of the treatment period to Week 2 of the treatment period: The first day of the treatment period (Day 1) to Day 14
  - Week 2 of the treatment period to Week 4 of the treatment period: Day 15 to Day 28
  - The same shall apply thereafter, and the final period between the scheduled study visits should be Week 20 to Week 24 of the treatment period: Day 141 to a blood sampling day for hematological tests at Week 24 of the treatment period. However, for subjects who discontinued their treatment, the final period between the scheduled study visits should be up to the day before discontinuation.
- \*3: If there are multiple applicable doses, the sum of the calculated values for each dose should be used.
- \*4: For subjects who discontinued their treatment, the final period between the scheduled study visits (days) should be the actual number of days until the day before discontinuation.
- \*5: In this tabulation, 1 month is counted as 30.4375 days ( $365.25/12 = 30.4375$ ).

#### 4.14Kt/V

Kt/V is defined by the following equation. It is calculated based on the first day of treatment period, Week 24, and the day of discontinuation. All items used for the calculation of Kt/V should be those measured on the same day.

$$Kt/V = -\ln(Ct/C0 - 0.008 \times t) + (4 - 3.5 \times Ct/C0) \times (BW0 - BWt)/(BWt)$$

t: Dialysis time, C0: BUN concentration before dialysis, Ct: BUN concentration after dialysis, BW0: Body weight before dialysis, BWt: Body weight after dialysis

#### 4.15QOL (EQ-5D-5L) index value

Responses to five questions (mobility [Mo], self care [Sc], usual activities [Ua], pain/discomfort [Pd], anxiety/depression [Ad] in 5 levels (level 1 is healthy and the level goes up to 5, and the health status decreases with increases in level) are converted into index values. The index value is calculated using the Japanese EQ-5D-5L conversion table (Table 4.15.1) [1].

- (1) The responses to questions from Mo to Ad should be arranged side by side into five numbers (hereinafter, health state). The health state can exist from “11111” to “55555”.

- (2) If all five responses are 1, i.e. the health state is “11111”, the index value is 1. If the health state is other than “11111”, “Constant term: -0.060924” in Table 4.15.1 and the estimated value of the coefficient for each level of the response to each question should be used to obtain the index value using the following formula. The index value of the subject should be missing if one of the 5 questions has not been answered.

Index value = 1 + “Estimate of the constant term” + “Sum of ‘estimated coefficients corresponding to levels of responses other than 1’”

Table 4.15.1 Japanese EQ-5D-5L conversion table

Item	Level	Estimate	Standard error	p value
Constant term		-0.060924	0.013625	<0.0001
Mo	2	-0.063865	0.008996	<0.0001
	3	-0.112618	0.009287	<0.0001
	4	-0.179043	0.010231	<0.0001
	5	-0.242916	0.009425	<0.0001
Sc	2	-0.043632	0.008931	<0.0001
	3	-0.076660	0.009972	<0.0001
	4	-0.124265	0.010129	<0.0001
	5	-0.159659	0.008924	<0.0001
Ua	2	-0.050407	0.009205	<0.0001
	3	-0.091131	0.010005	<0.0001
	4	-0.147929	0.009744	<0.0001
	5	-0.174786	0.009115	<0.0001
Pd	2	-0.044545	0.008354	<0.0001
	3	-0.068178	0.010052	<0.0001
	4	-0.131436	0.008985	<0.0001
	5	-0.191203	0.009604	<0.0001
Ad	2	-0.071779	0.009701	<0.0001
	3	-0.110496	0.010863	<0.0001
	4	-0.168171	0.009850	<0.0001
	5	-0.195961	0.009164	<0.0001

Mo: mobility, Sc: Self care, Ua: Usual activities, Pd: Pain/discomfort, Ad: Anxiety/depression

### 4.16QOL (KDQOL) scoring

Step 1 (See Table 4.16.1[2]): The appropriate score is converted from the response choices for each item number in Table 4.16.1 [2] (See Listing 16.2.4.9 for questions) for each subject.

Table 4.16.1 Step 1 in KDQOL scoring [2]

Item number	Response choices	Score
Question 4 A–D Question 5 A–C, Question 21	1	0
	2	100
Question 3 A–J	1	0
	2	50
	3	100
Question 19 A, B	1	0
	2	33.33
	3	66.66
	4	100
Question 10 Question 5 A, C Question 12 A–D	1	0
	2	25
	3	50
	4	75
	5	100
Question 9 B, C, F, G, I Question 18 B	1	0
	2	20
	3	40
	4	60
	5	80
	6	100
Question 20	1	100
	2	0
Question 1, Question 2, Question 6, Question 8 Question 11 B, D, Question 14 A–M Question 15 A–H, Question 16 A, B Question 24 A, B	1	100
	2	75
	3	50
	4	25
	5	0
Question 7 Question 9 A, D, E, H Question 13 A–F Question 18 A, C	1	100
	2	80
	3	60
	4	40
	5	20
	6	0
Question 23	1	100
	2	83.33
	3	66.66
	4	50
	5	33.33
	6	16.66
	7	0

Step 2 (See Table 4.16.2[2]): The mean of the scores calculated at Step 1 in the item numbers in the right column of Table 4.16.2[2] is calculated for each subject by subscale. For questions 17 and 22, the scores obtained are multiplied by 10 to convert the values from 0 to 100. The mean value should be the score for each subject by subscale. If at least one question constituting the subscale is answered,

the subscale should be tabulated without missing. If “No” is chosen in question 16, the question 16 should be treated as missing.

Table 4.16.2 Step [2 in KDQOL scoring [2]

- Each item score should be averaged to calculate each subscale score

Subscale	Number of items	After scoring according to Table 4-1, the mean of the items included in each subscale should be calculated.
Kidney disease-specific scale		
Symptoms	12	Questions 14 A–K, L (M)*
Effects of kidney disease on daily life	8	Question 15 A–H
Burden due to kidney disease	4	Question 12 A–D
Working status	2	Question 20, Question 21
Cognitive function	3	Question 13 B, D, F
Relationship with people	3	Question 13 A, C, E
Sexual function	2	Question 16 A, B
Sleep	4	Question 17, Question 18 A–C
Social support	2	Question 19 A, B
Encouragement from dialysis staff	2	Question 24 A, B
Patient satisfaction with dialysis care	1	Question 23
Comprehensive scale (SF-36)		
Physical functioning	10	Question 3 A–J
Daily role functioning (physical)	4	Question 4 A–D
Bodily pain	2	Question 7, Question 8
General health	5	Question 1, Question 11 A–D
Vitality	4	Question 9 A, E, G, I
Social functioning	2	Question 6, Question 10
Daily role functioning (emotional)	3	Question 5 A–C
Mental health	5	Question 9 B, C, D, F, H

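### The KDQOL item-scoring table lists Question 5 A and C twice and Question 11 A and C not at all, so the General health subscale cannot be scored as defined

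*SAP*

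**What the plan says.** SAP section 4.16 scores the KDQOL in two steps. Step 1 (Table 4.16.1) converts each answer to a score between 0 and 100. Step 2 (Table 4.16.2) takes "The mean of the scores calculated at Step 1 in the item numbers" assigned to each subscale.

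The entries that matter are:

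- Table 4.16.1, two-level row (answer 1 = 0, answer 2 = 100): "Question 4 A–D Question 5 A–C, Question 21".
- Table 4.16.1, ascending five-level row (0, 25, 50, 75, 100): "Question 10 Question 5 A, C Question 12 A–D".
- Table 4.16.1, descending five-level row (100 to 0), the only row that names Question 11: "Question 11 B, D, Question 14 A–M".
- Table 4.16.2, General health, five items: "Question 1, Question 11 A–D".
- Table 4.16.2, role functioning (emotional), three items: Question 5 A to C.

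Section 4.16 also tabulates a subscale as non-missing once any one of its questions has been answered. SAP section 7.5.2 (12) sends the subscale scores to descriptive statistics, paired t-tests and an MMRM of change from the first day of treatment.

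**The concern.** Question 5 A and C have two scoring rules that disagree: answer 2 is worth 100 in one row and 25 in the other. Question 11 A and C have no rule, although General health needs them. A programmer who follows the table cannot produce the five-item General health score that the same section defines, and a reader cannot reproduce it from the SAP.

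Both absolute scores and changes are reported (Table 14.2.3.13.4.1 in the errata's list of output tables). An offset in General health that is stable over time would cancel in the changes but would remain in the absolute scores. The March 2019 errata correct other typographical slips in the SAP but not section 4.16. SAP section 9 lists only an unrelated addition of endpoints.

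**Working it through.** **1. Match the items to the rows.** Each item in the 19 subscales of Table 4.16.2 was matched to the rows of Table 4.16.1, with Symptoms counted as Question 14 A–L (12 items).

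| Items | Number | Rows in Table 4.16.1 |
|---|---|---|
| 5 A, 5 C | 2 | two |
| 11 A, 11 C | 2 | none |
| 17 | 1 | none, but Step 2 gives it a times-10 rule |
| All others | 73 | exactly one |
| Total | 78 | |

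The stated item counts in Table 4.16.2 agree with its item lists. General health is stated as 5 items, but only 3 of them (1, 11 B, 11 D) receive a Step 1 score.

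**2. Evidence for a misprint.**

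- Question numbers by row are 4, 5, 21; 3; 19; 10, 5, 12; 9, 18; 20; 1, 2, 6, 8, 11, 14, 15, 16, 24; 7, 9, 13, 18; 23. Only 10, 5, 12 fails to ascend.
- Other questions split across rows have complementary, complete letters. One row has "Question 9 B, C, F, G, I Question 18 B" and another has "Question 9 A, D, E, H Question 13 A–F Question 18 A, C". Question 9 is 5 + 4 = 9 letters (A–I), and Question 18 is 1 + 2 = 3 letters (A–C).
- Question 11 has only B and D. The letters it lacks, A and C, are the ones duplicated under Question 5.
- Reading 11 for 5 in the five-level row removes all four anomalies: no item is then in two rows, and General health has 5 of 5 items scored.

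**3. General health with 3 items instead of 5.** Let M3 be the mean of the three scored items and M2 the mean of the two unscored items.

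- Difference = M3 − (3 × M3 + 2 × M2)/5 = 0.4 × (M3 − M2).
- Extreme case: M3 = 100 and M2 = 0 gives 100 against 60, a difference of 40 points.
- One level (25 points) on a scored item: 25/5 = 5.0 on the defined scale, 25/3 = 8.3 on the three-item mean.
- One level on 11 A or 11 C: 5.0 on the defined scale (if the five-level row is meant for them), 0 on the three-item mean.
- All five items improve by one level: both versions change by 25, so there is no error.
- If M3 − M2 is the same at baseline and follow-up, the error cancels in the change score.

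**4. Role functioning (emotional).** Under the two-level row nothing changes. If A and C took the five-level row while B stayed on two levels:

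| Answers (A, B, C) | Two-level for all | Five-level for A and C |
|---|---|---|
| 1, 1, 1 | 0 | 0 |
| 1, 1, 2 | 33.3 | 8.3 |
| 1, 2, 1 | 33.3 | 33.3 |
| 1, 2, 2 | 66.7 | 41.7 |
| 2, 1, 1 | 33.3 | 8.3 |
| 2, 1, 2 | 66.7 | 16.7 |
| 2, 2, 1 | 66.7 | 41.7 |
| 2, 2, 2 | 100 | 50 |

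Six of the eight patterns would be lower, four by 25 points and two by 50. This mixed scoring is unlikely.

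**The case against.** The three-item result is only one reading. The partial-score rule in section 4.16 deals with unanswered questions, whereas 11 A and C may be answered and simply have no conversion. SAP section 6.1 makes a derived variable missing when any required value is missing, and on that rule General health would be missing for every subject. A programmer could also have gone to the manual cited for both tables and scored the items correctly. The SAP is a translation, so the slip may exist only in the English text. No wrong result has been shown, and the matter concerns one or two subscales of an other endpoint in an uncontrolled study of 20 subjects.

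Much of this stands as a limit on the consequences. The programming is unknown, the translation possibility is real, and the sizes in step 3 hold only for the three-item reading. None of it repairs the text. The rule specific to the KDQOL favours the three-item score, the general rule gives no score at all, and neither gives the defined five-item scale. A cited manual helps someone who notices the slip, but section 7.5.2 (12) directs the analysis to section 4.16.

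**Conclusion.** The concern holds. Table 4.16.1 is wrong as written: it gives two rules for Question 5 A and C and none for Question 11 A and C. Followed as written, with the section 4.16 rule for partial subscales, General health rests on 3 of its 5 items and is off by 0.4 × (M3 − M2). That error can be nil when the items move together and cannot exceed 40 points. Role functioning (emotional) is ambiguous on paper but unaffected under the two-level row, which covers all of Question 5 A–C and is probably the intended one.

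The misprint diagnosis is an inference from the table's own structure, because the questionnaire and the manual are not in the documents. Whether any reported score is affected depends on how the scoring was programmed. The scope is 2 of 19 KDQOL subscales, mainly General health. It should be corrected, but it does not bear on the haemoglobin or safety conclusions.

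**What to change.** Check the five-level row against the cited KDQOL scoring manual, including the scoring direction for Question 11 A and C, and against the Japanese original of the SAP. If confirmed, issue an erratum that replaces Question 5 A, C with Question 11 A, C in that row of Table 4.16.1. If the Japanese text is already right, correct only the translation.

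Then check how General health and role functioning (emotional) are coded in the scoring program, and re-run those two subscales only if they were coded from the misprinted table. The cost is one line in the errata and a check of two subscales.

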#### 4.17 Adverse drug reaction

Adverse events for which a causal relationship to the study drug was evaluated as “reasonably possible” are defined as adverse drug reactions.

### 5. Analysis Sets

Efficacy analysis will be performed in the full analysis set (hereinafter, FAS). Safety analysis will be performed in the safety analysis set.

The analysis sets are defined below; however, details of the handling of subjects should be determined by the sponsor by the time the data are fixed.

## **5.1 Efficacy analysis set**

The analysis set consisting of all subjects transitioned to the treatment period excluding the following subjects is the FAS.

- Subjects who did not have anemia associated with HD-CKD
- Subjects who have never received a dose of study drug
- Subjects with no efficacy data after the first day of study drug administration

## **5.2 Safety analysis set**

The analysis set consisting of all subjects transitioned to the treatment period excluding the following subjects is the safety analysis set.

- Subjects who have never received a dose of study drug
- Subjects with no safety data after the first of study drug administration

## **6. Data Handling**

Data should be handled as follows:

### **6.1 Handling of missing data**

If test measurements are missing or if problems with samples etc. result in invalid measurements or reference values, these should be handled as missing values. Derived variables should also be treated as missing if even one test value or other data required for derivation is missing or not adopted.

### **6.2 Handing of data for tabulation at each evaluation time point**

Data that meet the permitted range specified in the “Table 9.1-1 Permitted range of study visits” section of the protocol should be used for the tabulation at each evaluation time point and should not be imputed with those outside the permitted range.

If there are multiple data within the permitted range, then the one closer to the reference date should be adopted. If the deviations from the reference date are the same, data for the efficacy and safety evaluations should be adopted before and after the reference date, respectively.

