- [c] Not required if withdrawn prior to the treatment period.
- [d] To be performed prior to the study drug treatment (AE investigation begins after study drug administration).
- [e] Fundoscopy and chest X-ray performed once during screening period, once during Weeks 20–24 of treatment period. In the case of discontinuation of the treatment period, fundoscopy and chest X-ray should be performed within 14 days after discontinuation whenever possible.
- [f] Body weights should be measured before and after dialysis.
- [g] To be measured before dialysis on the day of dialysis during the screening period.
- [h] Tests during the treatment period should be performed before dialysis on the day of dialysis.
- [i] To be performed only in female subjects of childbearing potential.
- [j] Hb levels should be measured in blood collected in the supine position.
- [k] Only Hb levels should be measured.
- [l] Only urea nitrogen levels should be measured before and after dialysis on the first day, Week 24 of the treatment period, and on the day of treatment discontinuation.
- [m] To be measured in the sitting position after a 5-minute rest before blood sampling whenever possible.
- [n] To be measured in the supine position after a 5-minute rest before blood sampling whenever possible.
- [o] For subjects giving consent to blood sampling for genetic analysis, blood will be collected once as early as possible after Week 2 of the treatment period.
- [p] MT-6548 Tablets should be prescribed depending on the number of unused tablets by the subject. Subjects should be instructed to open a new bottle after using up the tablets in one bottle.
- [q] In principle, dosage adjustments should be performed at scheduled visits; however, an unscheduled visit may be provided for dosage adjustment, if considered necessary, in cases where excessive increases or decreases in Hb levels are of concern based on the Hb time course.

If tests and observations cannot be performed on the scheduled day, they may be performed within the permitted ranges shown below. During the treatment period, subjects are to visit the study site on the day of dialysis after a 2-day interdialytic interval; however, if this is difficult, subjects are to visit the study site on the day of dialysis after a 1-day interdialytic interval.

Table 9.1-1 Permitted ranges for study center visits

Evaluation timepoint		Reference date	Permitted range
Screening period* ¹	First day	–	–
	Visit 2	–	–

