Treatment period	First day* ²	Day 0	–
	Week 2	Day 14	Day 11–17
	Week 4	Day 28	Day 25–31
	Week 6	Day 42	Day 39–45
	Week 8	Day 56	Day 53–59
	Week 10	Day 70	Day 67–73
	Week 12	Day 84	Day 81–87
	Week 16	Day 112	Day 105–119
	Week 20	Day 140	Day 133–147
	Week 24	Day 168	Day 161–175
Day of discontinuation of treatment		Day of discontinuation	Within 7 days of discontinuation* ³
Follow-up observation period	Day of completion	Week 24 of treatment period (or day of discontinuation of treatment period)	14–21 days

*1: Maximum screening period length is 6 weeks. Re-testing may be performed as necessary.

*2: The first day of the treatment period is defined as the day the investigator/subinvestigator determined the subject to be “suitable” to start the treatment period.

*3: Fundoscopy and chest X-ray to be performed to extent possible within 14 days of study withdrawal.

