Fundoscopy will be performed once each within the screening period, from treatment period Week 20 to Week 24, and to extent possible within 14 days of study withdrawal. An ophthalmologist will perform the fundoscopy and make evaluations according to the 3-point scale below. Ophthalmologist evaluations will be recorded in CRFs. Fundoscopy images and ophthalmologist evaluations will be stored at study centers.

- 1) Normal
- 2) Clinically non-problematic abnormality
- 3) Clinically problematic abnormality (retinal hemorrhage yes/no, retinal oedema yes/no)

(8) Chest X-ray

Fundoscopy will be performed once each within the screening period, from treatment period Week 20 to Week 24, and to extent possible within 14 days of study withdrawal. Investigators/subinvestigators will evaluate test results according to the 3point scale below. Evaluation results will be recorded in CRFs. Chest X-rays will be stored at the study center.

- 1) Normal
- 2) Clinically non-problematic abnormality
- 3) Clinically problematic abnormality

(9) Pregnancy tests (only for women who may become pregnant)

Blood sampling and pregnancy testing will be performed on the first day of the screening period, treatment period Week 24, and the day of discontinuation of treatment. Investigators/subinvestigators will evaluate pregnancy based on test results and interview when appropriate. Evaluation results will be recorded in CRFs. If the subject is incapable of becoming pregnant, the reason for this will be recorded in CRFs (women only).

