13.2 Data handling

(1) Definition of missing values

If test measurements are missing or if problems with samples etc. result in invalid measurements or reference values, these are handled as missing values.

(2) Handling of timepoint data for statistical summaries at each measurement timepoint

Statistical summaries for each evaluation timepoint will use data compliant with permitted ranges as described in “Table 9.1-1 Permitted ranges for study center visits.” There will be no supplementing with data from outside the permitted range.

If multiple data points exist within the permitted range, then the one closest to the scheduled day will be used. If there are deviations from the scheduled day, then data points prior to the scheduled day will be used for efficacy evaluation, and data points after the scheduled day will be used for safety evaluation.

(3) Handling of efficacy endpoints if rescue therapy was implemented

No data obtained after implementation of rescue therapy will be used for efficacy evaluation.

(4) Imputation of missing values

Missing values for treatment period Week 24 will be imputed by last observation carried forward (LOCF). Data from treatment period Week 24 with missing values imputed will be used as data from the completion of treatment period.

Required regulations for data handling other than those enumerated above will be described in the statistical analysis protocol prior to data lock.

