- [b] The scheduled study visit during the treatment period shall be the dialysis day 2 days after the previous dialysis, and if it is difficult, the dialysis day 1 day after the previous dialysis.
- [c] Should not be performed if discontinued before the treatment period.
- [d] Should be performed before study drug administration (AE investigations begin after study drug administration).
- [e] Fundoscopy and chest X-ray should be performed once during the screening period. Should be performed once during Week 20 to Week 24 of the treatment period. Should be performed within 14 days after discontinuation whenever possible if discontinued during the treatment period.
- [f] Body weight should be measured before and after dialysis.
- [g] Measurements on the day of dialysis should be performed before dialysis during the screening period.
- [h] Tests during the treatment period should be performed before dialysis on the day of dialysis.
- [i] To be performed only in female subjects of childbearing potential.
- [j] Hb values should be measured in blood collected in the supine position.
- [k] Only Hb values should be measured.
- [l] Urea nitrogen levels should be measured only before and after dialysis on the first day, Week 24 of the treatment period, and on the day of treatment discontinuation.
- [m] Measurements should be made before blood sampling as much as possible. Measurements should be made in the sitting position after 5 minutes of rest.
- [n] Measurements should be made before blood sampling as much as possible. Measurements should be made in the supine position after 5 minutes of rest.
- [o] Blood should be collected once as early as possible after Week 2 of the treatment period for subjects who have given consent to the genetic analysis tests.
- [p] MT-6548 tablets should be prescribed to subjects depending on the number of their unused tablets. Subjects should be instructed to use up one bottle before opening the next.
- [q] In principle, dosage adjustments should be performed at scheduled study visits; however, an unscheduled visit may be provided for dosage adjustment if considered necessary, in cases where excessive increases or decreases in Hb values are of concern based on the Hb value time course.

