#### **7.6.6 Fundoscopy**

The frequency of each decision result (normal, clinically nonsignificant abnormal, or clinically significant abnormal [presence or absence of retinal hemorrhage, presence or absence of retinal edema]) should be calculated at each evaluation time point, and a shift table composed of the decision

results (normal, clinically nonsignificant abnormal, or clinically significant abnormal) should be provided on the first day of the treatment period and each evaluation time point.

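### An on-schedule fundoscopy or chest X-ray on Day 148–160 falls in no SAP visit window and may be left out of the frequency and shift tables

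*SAP*

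**What the plan says.** **When the exams are done.** Footnote [e] to the protocol's schedule of tests reads: "Fundoscopy and chest X-ray performed once during screening period, once during Weeks 20–24 of treatment period". Footnote [e] in SAP 2.2 agrees: "Should be performed once during Week 20 to Week 24 of the treatment period". Protocol 9.2.4.1(7) repeats it for the eye exam: "Fundoscopy will be performed once each within the screening period, from treatment period Week 20 to Week 24". None of these ties the exam to a particular visit. (The chest X-ray item, 9.2.4.1(8), names fundoscopy in its timing sentence, apparently a copying slip. The X-ray timing therefore rests on footnote [e].)

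**Which data are tabulated.** Under SAP 6.2, data meeting the Table 9.1-1 ranges are "used for the tabulation at each evaluation time point and should not be imputed with those outside the permitted range". Protocol 13.2(2) says: "There will be no supplementing with data from outside the permitted range".

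**The ranges.** Table 9.1-1 gives Day 133–147 for Week 20 and Day 161–175 for Week 24. Its only entry specific to these exams is footnote *3, which covers discontinuation: "Fundoscopy and chest X-ray to be performed to extent possible within 14 days of study withdrawal".

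**The outputs.** SAP 7.6.6 says the frequency of each fundoscopy grade "should be calculated at each evaluation time point, and a shift table" is added. SAP 7.6.7 does the same for chest X-ray. Neither section names a Week 20–24 category. The SAP errata leave 6.2, 7.6.6 and 7.6.7 unchanged and keep the four affected tables (14.3.6.1, 14.3.6.2, 14.3.7.1, 14.3.7.2).

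**The concern.** The collection rule and the tabulation rule do not fit together. A site can follow the protocol exactly, examine a subject on Day 150, and produce a result that the tabulation rule places nowhere. Each completer has one scheduled on-treatment exam of each kind, so there is no second result to take its place.

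Protocol 5.3.2 says fundoscopy is included to assess the drug's effect on the fundus. The shift table is the planned summary that would show a move from normal to a non-problematic abnormality, because such a move is not by that grade alone an adverse event. If exams are omitted, the shift table loses those subjects, including any with problematic grades, and its denominator shrinks. In a study of 20 subjects a few omissions would be visible.

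A separate problem affects the exams that are kept. They are divided between a Week 20 row and a Week 24 row, so neither row describes all subjects, although the protocol intends one assessment.

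**Working it through.** **Inputs.** Reference days 140 (Week 20) and 168 (Week 24), and their permitted ranges, from Table 9.1-1. Planned N = 20 from protocol 6.1, set on feasibility. Exam timing from footnote [e].

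**1. Reproduce the plan's windows.** Reference day = 7 × week; range = reference day ± 7.
- Week 20: 140 ± 7 = Day 133–147, as stated.
- Week 24: 168 ± 7 = Day 161–175, as stated.

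**2. Find the gap.** First uncovered day = 147 + 1 = 148. Last = 161 − 1 = 160. Length = 160 − 148 + 1 = 13 days.

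**3. Look for a rule that would recover an exam in the gap.**
- Table 9.1-1 footnote *3 applies only after discontinuation.
- The Week 24 LOCF output in SAP 6.4 covers laboratory values, vital signs and QOL indices. These exams are not listed.
- Protocol 13.2(4) states a general Week 24 LOCF rule. It does not clearly help: 13.2(2) bars filling in from outside the range, the result is attached to no time point, and a completer has no earlier scheduled on-treatment exam to carry forward.

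**4. Size under an assumed booking pattern.** The documents give no booking dates. The even-spread columns assume exam days spread uniformly over the span and all 20 subjects completing.

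| | All exams at the Week 20 or 24 visit, within range | Even over Day 133–175 | Even over Day 140–168 |
|---|---|---|---|
| Days in span | – | 175 − 133 + 1 = 43 | 168 − 140 + 1 = 29 |
| Share in gap | 0 | 13/43 = 30.2% | 13/29 = 44.8% |
| Expected of 20 in gap | 0 | 20 × 13/43 = 6.0 | 20 × 13/29 = 9.0 |
| Expected of 20 in each of the two rows | depends on visit chosen | 20 × 15/43 = 7.0 | 20 × 8/29 = 5.5 |

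Under either even spread, the chance that at least one exam falls in the gap is above 99.9%: 1 − (30/43)^20 = 0.9993 and 1 − (16/29)^20 = 0.99999.

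**5. After the fix.** One window from Day 133 to Day 175 has 0 uncovered days, against 13 now.

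**The case against.** The strongest reply is that Table 9.1-1 is a table of visit ranges, introduced for tests that could not be done on their scheduled day. The on-treatment fundoscopy and X-ray have no scheduled day, only an interval. An analyst could fairly treat that interval as their evaluation time point and regard SAP 6.2 as a bar on filling a visit with stray data, not an order to discard an exam done on schedule. This has force, and it is why the point says such exams may drop out. It does not settle the matter. SAP 7.6.6 and 7.6.7 tabulate by evaluation time point, the phrase that brings in 6.2. Footnote *3 shows that the table does reach these exams. No Week 20–24 time point is defined anywhere.

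The schedule grids are not legible in the available text, so a merged Week 20–24 cell cannot be ruled out. It would not change the ranges that 6.2 points to. By-subject listings may also show these results, but listings do not repair the summary tables.

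Three stronger inferences are tempting and are not supported:

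- **Retinal harm could go unreported.** Under protocol 9.2.4.2, abnormalities judged clinically problematic are adverse events whatever the day, and protocol 9.2.4.1(7) records retinal haemorrhage and oedema under that grade.
- **Nearly every subject could be lost.** Nothing in the documents points to mid-interval booking as the norm. Use of an ophthalmologist makes a separate appointment plausible, no more.
- **The shift table has no baseline.** SAP 7.6.6 has it "should be provided on the first day of the treatment period and each evaluation time point", and the only pre-treatment exam is in screening. The closest-day rule in SAP 6.4 already covers this.

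**Conclusion.** The point stands as a conflict between two written rules. The 13-day gap is exact. How many exams it would catch is unknown: 0 if every exam coincides with a Week 20 or Week 24 visit inside its range, and about 6 to 9 of 20 under an assumed even spread with no dropout. Neither figure is a forecast.

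The consequence is limited to descriptive safety tables in an uncontrolled study. What could vanish from every summary table is normal and non-problematic grades. Problematic findings would still appear as adverse events but could be missing from the shift table and its denominator. No efficacy result or test is affected. The split of in-range exams between two rows does not depend on the gap and follows from tabulating by visit. The plan should be corrected, because following it literally gives an incomplete table from complete data.

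**What to change.** In SAP 6.2, and by reference in 7.6.6 and 7.6.7, define one Week 20–24 evaluation for fundoscopy and chest X-ray: any exam from Day 133 to Day 175 counts, shown in a single row. Keep the existing 14-day allowance for subjects who discontinue. State which result counts if an exam is repeated within the window, since 6.2 chooses by distance from a reference date and this window would have none. Naming the screening exam as baseline in 7.6.6 and 7.6.7 is optional wording.

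The cost is a few sentences in the SAP and one changed row label in four tables. It needs no new data and no change at sites. Protocol 13.4 sets out how to document the change. If it comes after data lock, the reason must be given and the results kept distinct from the original plan.
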